4.10 Patient Replacement

Any patient who signs consent but does not receive study treatment may be replaced. In addition, any study patient who receives Y-90 but discontinues prior to treatment with nivolumab can be replaced. This includes patients who cannot start nivolumab within 4 weeks of Y-90 treatment, who must come off study.

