4.2.2 Nivolumab

For the first 3 patients in Phase I, nivolumab will be administered at 80mg as an intravenous infusion over approximately 30 minutes (-5 minutes / +15 minutes) every 2 weeks (Day 1 & 15 of each cycle) until disease progression or intolerable toxicity.

Dose escalation to 240mg will be determined in the standard 3+3 fashion (detailed in section 4.3). All patients in Phase Ib will be treated at 240mg IV nivolumab if determined to be the MTD. Treatment will begin 7-14 days after Y-90 administration. Patients should have recovered from any side effects resulting from Y-90 treatment (to ≤G1 or baseline). If a patient is still experiencing side effects 14 days after Y-90 treatment, the patient’s nivolumab treatment may be delayed by up to 14 additional days at the physician’s discretion (maximum 4-week delay). Scans will need to be performed 21-28 days after Y-90 administration, and will fall during Cycle 1 of nivolumab. If a patient is not able to start nivolumab treatment within 4 weeks (28 days), the patient should come off study and be replaced.

Subjects may be dosed no less than 12 days from the previous dose. There are no pre-medications recommended for nivolumab on the first cycle. If an acute infusion reaction is noted, subjects should be managed according to Section 4.2.4.

Treatment will be administered on an outpatient basis. Reported adverse events and potential risks are described below. No investigational or commercial agents or therapies other than those described below may be administered with the intent to treat the patient’s malignancy.

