6.3 Secondary Endpoints

- For the purposes of this study, patients who have received at least one dose of nivolumab will be considered for evaluation of the safety and toxicity profile of the combination therapy. Safety and tolerability will be measured by the incidence of all adverse events, serious adverse events, deaths and laboratory abnormalities. Adverse event assessments and laboratory tests will be performed at baseline, and continuously throughout the study at the beginning of each subsequent cycle.
- All patients should be re-evaluated for response 21-28 days after Y-90 then every 8 weeks (every 12 weeks after 13 months) using RECIST criteria. Overall response will be calculated by sum of the complete and partial response rates according to measurement of target and non-target lesions as described below.
- Disease control rate will be determined at 24 months from the start of nivolumab treatment by the sum of complete response, partial response and stable response according to measurement of target and non-target lesions as described below.
- Patients who have a response sufficient enough where by shrinkage of the tumors allows them to be considered for transplant will be determined by established BCLC transplant guidelines for individual tumor sizes.
- PFS is defined as the duration of time from start of treatment to time of progression or death, whichever occurs first. Progression assessment will be performed by

investigator each time the patients has a radiologic evaluation after 8 weeks of treatment. OS is defined as the duration of time from start of treatment to time of death.

6.3.1 Definitions:

Evaluable for toxicity. All patients will be evaluable for toxicity from the time of their first treatment with nivolumab.

Evaluable for objective response. Only those patients who have measurable disease present at baseline, have received at least one dose of therapy, and have had their disease re-evaluated will be considered evaluable for response. These patients will have their response classified according to the definitions stated below. RECIST measurements should be used when available. When RECIST measurements cannot be made due to infiltrative disease, evaluable disease needs to be confirmed by pathology.

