10.2 Data Analyses Plans

Any subject who has received the investigational combination will be analyzed in an intention to treat format. The MTD will be determined as described in Section 4.3. Objective response rate (ORR = CR + PR) as defined in Section 6.3.3.1 and disease control rate (CR+PR+SD) will be calculated and a 95% confidence interval for response will be obtained using the methods of Porcher and Desseaux (2012) [37]. Progression-free survival will be summarized using the Kaplan-Meier product limit curve. Besides the required reporting of adverse events, adverse events will be summarized for all patients in the trial by type, duration, severity, timing and attribution (probable cause of adverse event). Whole exome sequencing and computational analyses will be performed to assess mutanome and immunome (subpopulations of immune cells). Change in clonal burden landscape of various mutanome and immunome will be analyzed to investigate its correlation with treatment response or development of resistance to treatment.

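### Section 10.2 labels its analysis intention to treat, but the set is combination-treated: patients given study Y-90 who never start nivolumab are replaced and left out, with no analysis of all who began the regimen

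*Combined protocol and SAP*

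**What the plan says.** Section 4.1 places Y-90 after study registration, and the section 5.0 schedule lists it as induction under the on-treatment columns. Nivolumab is planned 7-14 days later. Section 4.2.2 adds, with the delay counted in days: "If a patient is still experiencing side effects 14 days after Y-90 treatment, the patient’s nivolumab treatment may be delayed by up to 14 additional".

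Two sections deal with patients who never reach nivolumab:

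- Section 4.10: "any study patient who receives Y-90 but discontinues prior to treatment with nivolumab can be replaced". It continues: "This includes patients who cannot start nivolumab within 4 weeks of Y-90 treatment, who must come off study".
- Section 4.2.2: "If a patient is not able to start nivolumab treatment within 4 weeks (28 days), the patient should come off study and be replaced".

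Three places bear on who is analysed and from when:

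- Section 10.2: "Any subject who has received the investigational combination will be analyzed in an intention to treat format".
- Section 6.3.1, on response: patients with measurable disease at baseline who "have received at least one dose of therapy, and have had their disease re-evaluated will be considered evaluable for response". The agent is not named, whereas the toxicity definition just above it names nivolumab.
- Section 6.3: "PFS is defined as the duration of time from start of treatment to time of progression or death, whichever occurs first". It does not say whether treatment starts with Y-90 or with nivolumab.

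The efficacy plan contains no sensitivity analysis that includes Y-90-only patients, no rule for their response status, and no commitment to report how many were replaced.

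**The concern.** An intention-to-treat analysis of a two-step regimen keeps everyone who was assigned to it, or in a single-arm trial at least everyone who began it. Section 10.2 instead conditions on receipt of the second step. Whether a patient gets that far is settled after Y-90, and the only cause of a late start that section 4.2.2 describes is continuing side effects of Y-90. The set is therefore selected on a post-treatment event that may be related to outcome.

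The Phase Ib primary endpoint is affected. A reader told that the ORR is intention to treat will assume that patients who began the regimen and did not complete its first month are in the denominator. They are not, and without a reported count the reader cannot put them back. The proportion alive and progression free at 24 weeks has the same difficulty.

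**Working it through.** **1. Reproduce the design.** Inputs from section 10.1: null rate 10%, alternative 30%; 10 patients in stage 1, continue with 2 or more responses; positive with 6 or more of 29.

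Let X1 ~ Bin(10, p) and X2 ~ Bin(19, p). Early stopping = P(X1 ≤ 1). Positive result = P(X1 ≥ 2 and X1 + X2 ≥ 6).

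- Early stopping at p = 0.10: 0.3487 + 0.3874 = 0.736 (plan: 74%).
- Positive at p = 0.10: 0.0471 (plan: 5%).
- Positive at p = 0.30: 0.805 (plan: 80%).

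The plan's figures are reproduced. They describe the response rate p among the patients who are counted, that is, those who reach nivolumab.

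**2. Relate the two populations.** Let d be the share of Y-90-treated patients who never start nivolumab. Then

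ORR(all Y-90) = (1 − d) × ORR(combination-treated) + d × ORR(non-starters).

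The combination-treated ORR exceeds the all-Y-90 ORR exactly when non-starters respond less often than starters. The figures below take the extreme case in which no non-starter responds.

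**3. Choose d.** The documents give no value. The only related figure is the accrual margin in section 10.1, 40 − 38 = 2 patients for unevaluable patients of every kind. I take k = 1, 2 or 3 replaced patients beside 29 analysed, so d = k/(29 + k), and add 10% and 15% to show the trend. All of these are assumptions.

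**4. Effect on the smallest positive result.**

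| k | d | ORR with non-starters counted |
|---|---|---|
| 0 | 0% | 6/29 = 20.7% |
| 1 | 1/30 = 3.3% | 6/30 = 20.0% |
| 2 | 2/31 = 6.5% | 6/31 = 19.4% |
| 3 | 3/32 = 9.4% | 6/32 = 18.8% |

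**5. Chance of a positive result when the all-Y-90 ORR is 10%.** The combination-treated rate is then 0.10/(1 − d), and the two-stage sum in step 1 is evaluated at that rate.

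| d | Combination-treated rate | P(positive) |
|---|---|---|
| 0% | 10.0% | 4.7% |
| 3.3% (k = 1) | 10.3% | 5.4% |
| 6.5% (k = 2) | 10.7% | 6.1% |
| 9.4% (k = 3) | 11.0% | 6.9% |
| 10% | 11.1% | 7.1% |
| 15% | 11.8% | 8.8% |

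The 15% row needs about five non-starters (29/0.85 ≈ 34, and 34 − 29 = 5), beyond the 1 to 3 considered in step 4.

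**The case against.** The strongest reply is that the design tests what it says it tests. Section 2.1.2 asks for ORR to the combination, section 10.1 counts evaluable patients, and section 10.2 openly restricts the set to recipients of the combination. A treated-set analysis is common and usable in a single-arm Phase Ib study. This stands: a reader might infer that the 5% type I error is broken, and it is not. It holds for the combination-treated population. What fails is the label, and the absence of any figure for the regimen as started.

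A reader might also infer that ORR and 24-week progression-free survival are certainly biased upward because only the fittest reach nivolumab. The documents do not establish that:

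- Y-90 is itself active, and section 4.2.1 says its maximal effect may appear only at 3 months, so a non-starter could respond.
- Patients may leave for withdrawn consent or administrative reasons (section 4.9), unrelated to prognosis.
- Radiographic progression is largely not a route to exclusion on the planned schedule. The first post-Y-90 scan is at 21-28 days, after nivolumab should have begun, so it matters only for delayed patients.

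Nor is it settled that section 6.3.1 excludes Y-90-only patients. If therapy there includes Y-90, a patient with a follow-up scan could be evaluable for response under 6.3.1 while outside the set in 10.2.

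Finally, disease control rate might seem to need the same treatment. Its definitions run from the start of nivolumab, so a non-starter has no time zero, and including such patients would redefine the endpoint.

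Some of the information is already gathered. Reasons for discontinuation are documented (section 4.9), and section 4.8 follows early discontinuers to week 24 from the start of study treatment. It is unclear whether that applies to patients "who cannot start nivolumab within 4 weeks of Y-90 treatment, who must come off study".

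**Conclusion.** The point holds as a mislabelled population with no companion analysis. The section 10.2 set is combination-treated and selected on an event after Y-90. Its ORR, and the 24-week proportion, are likely but not certainly higher than for all who start the regimen. The Simon rule and its error rates are right for the set it uses and should stay, but they cannot be quoted for all Y-90-treated patients.

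The size is modest and illustrative. Within 1 to 3 replaced patients the smallest positive ORR falls by less than 2 percentage points, and the chance of a positive result at a 10% all-Y-90 ORR rises by up to about 2 points. Both results assume the number of non-starters and that none of them responds. The larger values in the working need attrition that nothing in the documents supports or rules out. The change should be made because it concerns the primary endpoint, costs little, and cannot be supplied by a reader afterwards.

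**What to change.** 1. In section 10.2, replace the intention-to-treat wording with a named combination-treated set, and keep that set for the Simon decision.
2. Add a sensitivity analysis of ORR and of the proportion alive and progression free at 24 weeks in all registered patients who received study Y-90 at the Phase Ib dose assignment. Count non-starters without a documented response as non-responders, and time progression-free survival from Y-90. Leave disease control rate out.
3. Report how many patients were replaced after Y-90, and why.
4. State in section 6.3.1 whether therapy includes Y-90 alone, and reconcile that definition with section 10.2.
5. State in section 4.8 that follow-up to week 24 covers Y-90-only patients, and align sections 4.2.2 and 4.10 with that where they take such patients off study.

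The cost is wording in a few sections, one extra line for each of two endpoints, a figure likely to be slightly less favourable than the main one, and week-24 status for a few more patients. The sample size and the decision rule do not change.

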5.0 STUDY PROCEDURES

	Screening ¹	On Treatment (1 cycle = 28 days)				Off Treatment		
Time Period	Baseline	Induction Treatment ⁹	Cycle 1 ¹⁰ (± 3 days)		Cycle 2+ (± 3 days)		End of Treatment ¹³	Follow-up ¹⁴
			D1	D15	D1	D15		
Assessment or Activity								
Informed Consent	X							
Medical history	X							
Physical exam ²	X		X		X			
ECOG status	X		X		X			
Adverse Events & ConMeds	X	X	X		X		X	X
Tumor Measurement ³	X		X ³		X ³			
Coagulation studies (INR, PT, PTT) ⁴	X ⁴							
Child-Pugh Class	X		X					
CBC with diff ⁵	X ⁵		X	X	X	X	X	
Chemistry panel ⁶	X ⁶		X	X	X	X	X	
AFP	X		X		X			
TSH with reflex T3, T4			X		X			
Hepatitis Panel ⁷	X						X	
Urinalysis	X						X	
Pregnancy Test ⁸	X	X	X				X	
ECG	X							
Angiogram ⁹	X							
Y-90 ⁹		X						
Nivolumab ¹⁰			X	X	X	X		
Correlative studies ¹¹	X		X		X ¹¹			
Archival tissue collection ¹²	X							
Survival status ¹⁴								X

1 All screening procedures should take place within 28 days of registration unless noted otherwise.

2 Includes vital signs (pulse, respirations, blood pressure), height (baseline only) and weight.

- 3 Imaging will be performed at screening, 21-28 days after Y-90 administration (during Cycle 1), and every 2 cycles (starting with Cycle 3 Day 1, ± 7 days) for the first 13 months. Imaging will then occur every 3 cycles (± 7 days) until disease progression or treatment discontinuation. Imaging will include either CT of Chest/Abdomen/Pelvis or MRI as indicated. Contrast should be used to the greatest extent possible (see section 6.1 for details).
- 4 Coagulation studies will be performed at the time of the screening angiogram. Patients who are on Coumadin will require their INR to be checked every cycle or according to the treating oncologist. If patient is on low molecular weight heparin, an Anti-Xa level should be tested to ensure it is within therapeutic range
- 5 CBC with differential will include WBC, ANC, ALC, Platelets, and Hemoglobin. CBC should be collected within 14 days prior to registration and reviewed prior to each nivolumab treatment.
- 6 Chemistry panel will be drawn at screening (within 14 days prior to registration) and pre-dose at all treatment visits. Chemistry panel will include glucose, calcium, albumin, ALT, AST, sodium, potassium, total bilirubin, alk phos, and creatinine.
- 7 Full hepatitis panel at screening including HBsAg, HBeAg, and HBV DNA. If active hepatitis will need to see hepatologist and begin treatment prior to starting on study. Patient should have viral load < 100 IU/mL prior to nivolumab infusion. See inclusion criteria 3.1.5 for hepatitis B requirements for eligibility.
- 8 FOCBP can have either a serum or urine pregnancy test within 7 days prior to registration (note: this may be completed as part of the angiogram), prior to Y-90 treatment (pregnancy testing is a standard procedure before Y-90), and within 24 hours prior to starting nivolumab treatment (scheduled for C1D1).
- 9 Prior to registration, patients will undergo a planning angiogram in IR to determine doses of Y-90. Since Y-90 administration is usually planned around 7 days from the angiogram, screening procedures and registration should be planned accordingly.
- 10 Patients will receive IV nivolumab starting with Cycle 1 Day 1, which is planned 7-14 days after the induction Y-90 procedure to allow for count recovery (Note: Patients can be treated with nivolumab up to 4 weeks after Y-90 in the case of TB or continuing side effects). During this break, patient will be evaluated by a medical oncologist as part of standard procedures. Starting with Cycle 1 Day 1, patients will begin treatment with intravenous nivolumab as maintenance either at 80mg or 240mg over 30 minutes (-5 minutes / +15 minutes) every 2 weeks (Day 1 & 15 of each cycle). Treatment will continue until disease progression, intolerable side effects, or patient withdraws consent or is removed from the study for any other reason.
- 11 Correlative blood work will be collected for all patients in a 10mL NaHep tube at baseline, post Y-90 treatment (pre-dose on Cycle 1 Day 1) and during nivolumab treatment as follows: pre-dose every 8 weeks for the first 24 weeks (C3D1, C5D1, and C7D1), and every 16 weeks thereafter (every 4 cycles starting with C11D1). This will be used for peripheral lymphocyte analysis and correlative studies as detailed in the protocol.
- 12 If patient has archival tissue present, it will be collected after registration for next-generation sequencing (NGS) and immunohistochemistry as described in section 9.0 and the separate lab manual.
- 13 An End of Treatment visit should occur 30 days (+/- 7 days) after the last dose of nivolumab.
- 14 Patients will be followed for survival for up to 2 years after treatment discontinuation. If a patient discontinues treatment prior to 24 weeks (6 cycles), they should undergo follow-up (either by routine clinic visit or by phone call) every 2 weeks until the end of the 24-week period from start of study treatment to document survival and disease progression. After this period, patients should be followed for survival every 6 months for 2 years (by routine clinic visit or phone call). Patients should also be followed for SAE's for 100 days after discontinuing study drug.

6.0 ENDPOINT ASSESSMENT

6.1 Definitions

Response and progression will be evaluated in this study using the new international criteria proposed by the revised Response Evaluation Criteria in Solid Tumors (RECIST) guideline (version 1.1) [6]. Changes in the largest diameter (unidimensional measurement) of the tumor lesions and the shortest diameter in the case of malignant lymph nodes are used in the RECIST criteria.

High resolution CT with oral/intravenous contrast or contrast-enhanced MRI is the preferred imaging modalities for assessing radiographic tumor response. If a subject has a known allergy to contrast material, please use local prophylaxis standards to obtain the assessment with contrast if at all possible, or use the alternate modality. In cases where contrast is strictly contraindicated, a non-contrast scan will suffice. Screening assessments should be performed within 28 days of start of study treatment. If more than one method is used at screening, then the most accurate method according to RECIST 1.1 should be used when recording data, and should again be used for all subsequent assessments.

Radiographic tumor assessments will be conducted at screening, 21-28 days after Y-90 administration (during Cycle 1 of nivolumab), Cycle 3 Day 1 (± 7 days, 1 cycle = 28 days) and every 2 cycles (± 7 days) thereafter for the first 13 months. Imaging will then occur every 3 cycles (± 7 days) until disease progression or treatment discontinuation. Imaging will include either CT of Chest/Abdomen/Pelvis or MRI as indicated. Contrast should be used to the greatest extent possible. Tumor assessments for all subjects should continue as per protocol even if dosing is interrupted. Tumor measurements should be made by the same investigator or radiologist for each assessment whenever possible. Changes in tumor measurements and tumor responses to guide ongoing study treatment decisions will be assessed by the investigator using RECIST.

6.2 Primary Endpoint

The primary endpoint of this study is establishing the maximum tolerated dose for the combination therapy of nivolumab and Y-90. Patients who received at least one dose of nivolumab will be considered for evaluation.

6.3 Secondary Endpoints

- For the purposes of this study, patients who have received at least one dose of nivolumab will be considered for evaluation of the safety and toxicity profile of the combination therapy. Safety and tolerability will be measured by the incidence of all adverse events, serious adverse events, deaths and laboratory abnormalities. Adverse event assessments and laboratory tests will be performed at baseline, and continuously throughout the study at the beginning of each subsequent cycle.
- All patients should be re-evaluated for response 21-28 days after Y-90 then every 8 weeks (every 12 weeks after 13 months) using RECIST criteria. Overall response will be calculated by sum of the complete and partial response rates according to measurement of target and non-target lesions as described below.
- Disease control rate will be determined at 24 months from the start of nivolumab treatment by the sum of complete response, partial response and stable response according to measurement of target and non-target lesions as described below.
- Patients who have a response sufficient enough where by shrinkage of the tumors allows them to be considered for transplant will be determined by established BCLC transplant guidelines for individual tumor sizes.
- PFS is defined as the duration of time from start of treatment to time of progression or death, whichever occurs first. Progression assessment will be performed by

investigator each time the patients has a radiologic evaluation after 8 weeks of treatment. OS is defined as the duration of time from start of treatment to time of death.

6.3.1 Definitions:

Evaluable for toxicity. All patients will be evaluable for toxicity from the time of their first treatment with nivolumab.

Evaluable for objective response. Only those patients who have measurable disease present at baseline, have received at least one dose of therapy, and have had their disease re-evaluated will be considered evaluable for response. These patients will have their response classified according to the definitions stated below. RECIST measurements should be used when available. When RECIST measurements cannot be made due to infiltrative disease, evaluable disease needs to be confirmed by pathology.

Evaluable non-target disease response. Patients who have lesions present at baseline that are evaluable but do not meet the definitions of measurable disease, have received at least one dose of therapy, and have had their disease re-evaluated will be considered evaluable for non-target disease. The response assessment is based on the presence, absence, or unequivocal progression of the lesions.

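### Read literally, the PFS sentence in 6.3 leaves out the mandatory early scan, so a progression seen there would be dated about 4 to 8 weeks late

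*Combined protocol and SAP*

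**What the plan says.** Section 6.3 gives the definition: "PFS is defined as the duration of time from start of treatment to time of progression or death, whichever occurs first". The next sentence has the investigator assess progression "each time the patients has a radiologic evaluation after 8 weeks of treatment".

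An earlier scan is compulsory. Section 4.2.2 states: "Scans will need to be performed 21-28 days after Y-90 administration, and will fall during Cycle 1 of nivolumab". Section 6.1 and footnote 3 of the study calendar (5.0) put the same scan in the tumour assessment schedule: "Radiographic tumor assessments will be conducted at screening, 21-28 days after Y-90 administration (during Cycle 1 of nivolumab), Cycle 3 Day 1". Section 6.3 itself uses it: "All patients should be re-evaluated for response 21-28 days after Y-90 then every 8 weeks".

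Other sections recognise progression without a time limit:
- 6.1 applies RECIST 1.1 to both response and progression.
- 6.3.3.1 defines progressive disease against the smallest sum on study.
- 4.4.4 recognises an initial progression and has it re-evaluated at the next assessment, at least 4 weeks later.

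Section 10.2 summarises PFS by Kaplan-Meier and gives no rule for dating events or for censoring. The secondary objective in 2.2.1 is the proportion alive and progression free at 24 weeks.

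**The concern.** The definition and the assessment sentence point in different directions. Under the definition, a progression on the early scan is an event on that date. Under the assessment sentence taken literally, the early scan is not an occasion for assessing progression, so the event waits for a later scan. Two analysts could give the same patient different PFS dates, each citing the protocol.

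The error runs one way. Ignoring an early progression can only lengthen the recorded PFS time. In a single-arm trial no comparator shares the distortion, so the reported curve simply looks better than the scans showed.

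**Working it through.** The plan gives no figure on this point to reproduce, so the check is calendar arithmetic in days from Y-90, using nominal cycle days.

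**Inputs**
- Early scan: days 21-28 (4.2.2, 6.1).
- Nivolumab start, s: "Treatment will begin 7-14 days after Y-90 administration", so s = 7 to 14; "maximum 4-week delay" gives a latest s = 28.
- Cycle 3 Day 1 scan: s + 56, ± 7 days (28-day cycles; 6.1).
- Cycle 5 Day 1 scan: s + 112, ± 7 days.

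**Where the early scan falls on nivolumab.** With a routine start, 21 − 14 = 7 to 28 − 7 = 21. It is an on-treatment scan, before week 8 on either a Y-90 or a nivolumab clock.

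**Delay to the Cycle 3 Day 1 scan**

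| Nivolumab start | Scan window (s + 49 to s + 63) | Shortest delay | Longest delay |
|---|---|---|---|
| s = 7 | 56-70 | 56 − 28 = 28 | 70 − 21 = 49 |
| s = 14 | 63-77 | 63 − 28 = 35 | 77 − 21 = 56 |
| s = 28 | 77-91 | 77 − 28 = 49 | 91 − 21 = 70 |

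The delay is 28-56 days (4-8 weeks) with a routine start and up to 70 days (10 weeks) with the maximum delay. The shortest gap is 28 days, so Cycle 3 Day 1 always meets the 4-week minimum for the repeat evaluation in 4.4.4.

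**When Cycle 3 Day 1 does not qualify either.** The PFS bullet does not say whether treatment starts with Y-90 or nivolumab. On a nivolumab clock, a Cycle 3 Day 1 scan on days 49-55 is within its window but before 8 weeks. The next scan is Cycle 5 Day 1: day 112-126 after Y-90 for s = 7 and 119-133 for s = 14. The delay is then 112 − 28 = 84 to 133 − 21 = 112 days, or 12-16 weeks.

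**24-week proportion.** The latest Cycle 5 Day 1 scan is day 119 on a nivolumab clock, and 28 + 119 = 147 on a Y-90 clock. Both precede day 168. An early progression still present at either scan is therefore an event before week 24 under both readings, and the proportion does not change.

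It changes only if the early progression never becomes a recorded event. Let q be the share progressing on the early scan, f the share of those with no later scan and no recorded event (censored), and S the 24-week PFS of the other patients. The true value is (1 − q)S, and the Kaplan-Meier estimate is (1 − q)S / (1 − qf). The documents give none of q, f or S, so these values are assumptions:
- f = 0: no bias.
- S = 50%, q = 10%, f = 50%: 0.45 / 0.95 = 47.4% against 45.0%.
- S = 50%, q = 20%, f = 50%: 0.40 / 0.90 = 44.4% against 40.0%.
- Over q = 5-30%, f = 0-100%, S = 30-70%: from 0 to +21 points. The top (q = 30%, f = 100%, S = 70%) is 70% against 49%.

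This range shows how much depends on f. It is not an estimate for this trial.

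**The case against.** The strongest reply is that the sentence does not say that only later scans count. It says who assesses progression and when, and may loosely mean the 8-weekly scans. The definition before it excludes nothing, and 6.1, 6.3.3.1 and 4.4.4 would let an analyst count an early progression. That stands: this is an unresolved conflict in the text, not a settled rule to ignore early failures.

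A reader might go further in three ways that the documents do not support.

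- **That early progressors are lost from PFS.** Section 6.1 does run imaging "until disease progression or treatment discontinuation", but those words are in the sentence on 3-cycle imaging after 13 months. Section 4.8 requires contact every 2 weeks to week 24 after early discontinuation, expressly to record survival and progression. Section 4.4.4 provides a repeat evaluation, and deaths count on any reading. Some risk remains, because a contact may be a phone call, which cannot supply a RECIST measurement.
- **That a response on the early scan is banked while a progression is ignored.** Section 6.3.3.3 makes best response depend on confirmation as well as measurement, and closes the response window at progression.
- **That each lost event moves the 24-week proportion by 1/29 = 3.4 points.** The 29 are the Simon response cohort. Section 10.2 analyses anyone who received the combination, and up to 40 may enrol (1/40 = 2.5 points). The denominator is not fixed at 29.

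It can also be said that an early scan may show flare, which 6.3.3.3 anticipates, and that 4.2.1 says the full Y-90 effect may appear only at 3 months. That is a reason to use confirmation, which 4.4.4 already has. The protocol does not give it as a reason to leave the scan out of PFS.

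**Conclusion.** The point holds as a conflict of wording with a favourable dating bias if the PFS sentence is followed literally. The size is 4-8 weeks per early progression with a routine start, up to about 10 with the maximum nivolumab delay, and 12-16 in the nivolumab-clock case above. The Kaplan-Meier curve is held up between the early scan and the next qualifying scan. Median PFS lengthens if the curve would cross one half in that stretch.

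An effect on the 24-week proportion is possible but not established. It needs an early progression that is neither seen later nor otherwise documented, and its size cannot be derived from the documents.

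The consequence is minor. PFS is a secondary, descriptive summary without a hypothesis test, and the Phase Ib decision rests on response rate.

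**What to change.** In 6.3, delete the qualifier that restricts progression assessment to scans after 8 weeks, so that progression on any protocol scan, including the one 21-28 days after Y-90, counts for PFS. Add two rules to 10.2, for the PFS analysis only and with no bearing on treatment decisions:

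1. Where the repeat evaluation in 4.4.4 confirms progression, date the event at the first scan that showed it.
2. Count progression documented during the 4.8 follow-up as an event.

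The same edit should say whether the PFS clock starts at Y-90 or nivolumab, and state how patients without a recorded event are censored.

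The cost is a few lines of text and no added scans. PFS may look slightly less favourable, and some early flare may be counted as progression where confirmation is not obtained.
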